- d Hepatitis B surface antigen, hepatitis C virus antibody, human immunodeficiency virus (HIV) 1 antibody, HIV 2 antibody.
- A 5 tu purified protein derivative (PPD) skin test will be positive if ≥ 10 mm at 48 to 72 hours.
- These procedures are performed after study eligibility is confirmed (other than Day 1 tender and swollen joint counts). Hand/foot X-ray should be performed earlier, if required to confirm eligibility (Section 10.1, inclusion criteria #4).

Table 3-2 Schedule of Assessments: Treatment Period and Follow-up

Assessment/Event	Day 1 (Base- line) ^a	Week 2 ± 3 days	Week 4 (Synovial Biopsy Subset only) ± 3 days	Week 6 (MRI) ± 3 days	Week 8 ± 7 days	Week 12 (MRI) or Early Treatment Termination ± 7 days ^b	Safety Follow-up Visit 28 ± 7 days after last dose
Outpatient visit	X	X	X	X	X	X	X
Randomization and assignment of IVRS/IWRS subject ID number	X						
Verification of inclusion/exclusion criteria	X						
Study drug administration ^c	X	Continu	ious until We	ek 12 or Ear	ly Treatmen	t Termination	
Pill counts		X		X	X	X	
Weight, BMI	X			X		X	X
Physical examination ^d						X	X
Vital signs	X	X	X	X	X	X	X
12-lead ECG	X			X		X	
Adverse events and concomitant medications	X	X	X	X	X	X	X
Safety and Efficacy Laborato	ry Assessm	ents					
Serum chemistry	X	X		X	X	X	X
Hematology	X	X		X	X	X	X
Coagulation						X	
CRP and WESR	X	X	X	X	X	X	X
Rheumatoid factor and anti-CCP Antibodies	X					X	
Fasting lipid profile ^e	X^{f}	X		X		X ^f	X
Erythropoietin	X	X		X		X	X
Iron studies	X						
Urine pregnancy test (females of child-bearing potential only)	X					X	
Urinalysis						X	
Pharmacokinetic, Pharmacod	lynamic an	d Biomark	er Laboratoi	y Assessme	ents		
Plasma VX-509 PK	X^g			X^h		X^h	
Blood Biomarker Sample A	X	X		X		X	X
Blood Biomarker Sample B	X	X		X		X	X
Flow cytometry sample	X	X		X		X	X
Synovial Biopsy Subset only		·	1				
Diagnostic arthroscopy i	X^{j}		X				

Table 3-2 Schedule of Assessments: Treatment Period and Follow-up

Assessment/Event	Day 1 (Base- line) ^a	Week 2 ± 3 days	Week 4 (Synovial Biopsy Subset only) ± 3 days	Week 6 (MRI) ± 3 days	Week 8 ± 7 days	Week 12 (MRI) or Early Treatment Termination ± 7 days ^b	Safety Follow-up Visit 28 ± 7 days after last dose
Blood Biomarker Sample B			X				
Plasma VX-509 PK (in addition to samples collected on all subjects)			X^k				
Synovial Fluid (SF) samples (priority):	Synovial B	iopsy Subs	et only; as flu	iid volume	permits; all	ocated in descen	ding order of

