- 14. History of alcohol or drug abuse, or excessive alcohol consumption as determined by the investigator, during the previous 12 months before screening.
- 15. For female subjects: Pregnant or nursing; or planning to become pregnant during the study or within 90 days following the last VX-509 dose; or female subjects of childbearing potential who are unwilling or unable to use an acceptable method of contraception as outlined in this protocol from at least 14 days before the first dose of study drug and for 90 days following the last dose of study drug.
- 16. For male subjects: Subject has a female partner who is pregnant, nursing, or planning to become pregnant during the study or within 90 days following the last VX-509 dose; or male subjects who are unwilling or unable to use an acceptable method of contraception as outlined in this protocol from at least 14 days before the first dose of study drug and for 90 days following the last dose of study drug.
- 17. Subject is the investigator or a subinvestigator, research assistant, pharmacist, study coordinator, other staff, or a relative of study personnel directly involved with the conduct of the study.
- 18. Requirement for more than 1 NSAID after signing informed consent at screening (additional aspirin [second NSAID] ≤325 mg/day is allowed). The dose of any ongoing NSAID must be stable for at least 28 days before Day 1.
- 19. Systemic corticosteroid treatment (prednisone or equivalent) >10 mg/day. The dose of any ongoing systemic corticosteroid must be stable for at least 28 days before Day 1 (Section 16.13).
- 20. Allergy to gadolinium.
- 21. Prior treatment with a JAK inhibitor.
- 22. Other DMARDs (biologic/non-biologic) beyond the required DMARD for study entry must have been discontinued for specified minimum periods before screening (see Section 16.2). Subjects with prior treatment with rituximab/ocrelizumab (or other depleting monoclonal antibody) must show demonstrated recovery of any cytopenia(s).
- 23. Intraarticular corticosteroids in any joint within 4 weeks before screening, or within 12 weeks before screening for the MRI-designated hand or joint planned for arthroscopy.

- 24. Treatment with an investigational drug within 60 days or 5 half-lives preceding the first dose of study drug, whichever is longer.

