Serum follicle stimulating hormone (FSH) test: Serum FSH concentrations for 45- to 55-year-old postmenopausal females only (Screening Visit only). Levels must be within the laboratory's postmenopausal range for subjects to be eligible for the study.

Pregnancy β-human chorionic gonadotropin (β-HCG) testing: for females of child-bearing potential. Serum samples will be obtained during the Screening Visit and analyzed at the central lab. The urine pregnancy test before dosing on Day 1 will be performed at the site.

Additional clinical laboratory evaluations may be performed at other times if judged to be clinically appropriate.

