12.9.6.1 Contraception

At this stage in the development of VX-509, participation in this study (VX12-509-201) requires a commitment from the research subject and his/her partner to use 2 methods of birth control. Contraception for the couple is waived if the female partner is of non-childbearing potential (defined below) or in the rare case where the male partner is of non-childbearing potential (s/p orchiectomy).

Female Subjects of Non-Childbearing Potential:

To be considered of non-childbearing potential, the female subject must be:

- Postmenopausal: amenorrheic for at least 2 years and have a serum FSH level at screening within the laboratory's reference range for postmenopausal females; the FSH requirement is waived after age 60.
- Documented hysterectomy, or a bilateral oophorectomy/salpingo-oophorectomy.
- All other female subjects (including subjects with tubal ligations and subjects that do not have a documented hysterectomy) will be considered of childbearing potential.

Acceptable Contraceptive Methods:

Acceptable contraceptive methods for the **male** include the following:

- True abstinence, when this is in line with the preferred and usual lifestyle of the subject. Periodic abstinence (e.g., calendar, ovulation, symptothermal, post-ovulation methods) and withdrawal are not acceptable methods of contraception.
- Vasectomy 6 months or greater before the first dose of study drug, with a negative post-vasectomy semen analysis for sperm.
- Condom with spermicide (either as a single product if commercially available and/or allowed according to local regulations; otherwise condom and spermicide as separate products). This method should be in successful use at least 28 days before the first dose of study drug.
- Acceptable contraceptive methods for the **female** include the following:
- True abstinence, when this is in line with the preferred and usual lifestyle of the subject. Periodic abstinence (e.g., calendar, ovulation, symptothermal, post-ovulation methods) and withdrawal are not acceptable methods of contraception.
- Bilateral tubal ligation performed at least 6 months before the first dose of study drug.
- Oral, transdermal, injectable or implantable hormonal birth control method successfully used for at least 28 days before the first dose of study drug.

- An intrauterine device (hormone-releasing or non-hormone-releasing) in place for at least 90 days before the Screening Visit.

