12.9.6.2 Pregnancy

Subjects will be counseled to inform the investigator of any pregnancy that occurs during study treatment and for 90 days after the last dose of study drug.

If a subject or the female partner of a male subject becomes pregnant while participating in the study, study treatment must be permanently discontinued immediately. The investigator must notify the medical monitor and Vertex Global Patient Safety within 1 business day of the site's knowledge of the subject's (or partner's) pregnancy, by utilizing the Initial Pregnancy Notification Report Form.

If confirmed to be on active drug, the subject or partner will be followed until end of pregnancy and the infant will be followed for 1 year after the birth, provided informed consent is obtained from at least 1 parent. A separate informed consent form will be provided to explain these follow-up activities. Pregnancy itself does not constitute an adverse event.

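### No pregnancy test is scheduled between Day 1 and Week 12, so for an unnoticed, unreported pregnancy the stop-treatment rule has no scheduled trigger until dosing ends

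*Protocol*

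**What the plan says.** - **Schedule.** In Table 3-2 (Section 3), the row "Urine pregnancy test (females of child-bearing potential only" has a mark at Day 1 and at Week 12/Early Treatment Termination. Weeks 2, 4, 6 and 8 and the Safety Follow-up Visit are blank. Table 3-1 adds one serum test at screening.
- **Laboratory section.** Section 12.9.2 describes the screening serum test and says "The urine pregnancy test before dosing on Day 1 will be performed at the site". It adds no other scheduled on-treatment test. Anything further is discretionary: "Additional clinical laboratory evaluations may be performed at other times if judged to be clinically appropriate".
- **Stop rule.** Under Section 12.9.6.2, if a subject or a male subject's partner "becomes pregnant while participating in the study, study treatment must be permanently discontinued immediately". If active drug is confirmed and a parent consents, "the subject or partner will be followed until end of pregnancy and the infant will be followed for 1 year after the birth".
- **Reporting.** The same section says: "Subjects will be counseled to inform the investigator of any pregnancy that occurs during study treatment and for 90 days after the last dose".
- **Prevention.** Section 10.2 excludes "female subjects of childbearing potential who are unwilling or unable to use an acceptable method of contraception", and Section 12.9.6.1 says participation "requires a commitment from the research subject and his/her partner to use 2 methods of birth control".
- **Hazard.** Section 9.2.7 calls VX-509 teratogenic in rat and rabbit at doses at or above the human equivalents studied here, and says its effect on oral contraceptives is unstudied. Section 12.9.6 is milder: fetal variations in the rat only, at maternally toxic doses.

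**The concern.** The stop rule limits fetal exposure only if a pregnancy is found while the drug is still being taken. During dosing, the protocol's routes to finding one are the woman's own report and discretionary testing. Both need someone to suspect a pregnancy. The prevention measures make a pregnancy less likely but do not reveal one that has begun unnoticed. In the worst case, a conception soon after Day 1 that nobody suspects is exposed for most of the 12 weeks.

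All subjects already attend Weeks 2, 6 and 8 for serum chemistry and hematology, so the opportunity to test exists and is not used. The stake is individual fetal safety. No endpoint, estimate or error rate depends on it.

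**Working it through.** **Reading the table.** The columns are Day 1, Weeks 2, 4, 6, 8, Week 12/Early Treatment Termination and Safety Follow-up. Neighbouring rows confirm the reading: rheumatoid factor is marked at Day 1 and Week 12, and urinalysis at Week 12 only. Week 4 is a visit for the Synovial Biopsy Subset only, so the interim visits for all subjects are Weeks 2, 6 and 8. Windows are ±3 days at Weeks 2 and 6, and ±7 days at Weeks 8 and 12.

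**Gap between scheduled tests for a completer, in days.** The range adds the windows of the two visits that bound the gap.

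- Current schedule: 12 × 7 = 84; ±7 gives 77 to 91.
- Week 6 added: 42 ± 3 = 39 to 45, then 42 ± (3 + 7) = 32 to 52. Longest nominal gap 42.
- Weeks 2, 6 and 8 added: 14 ± 3 = 11 to 17; 28 ± (3 + 3) = 22 to 34; 14 ± (3 + 7) = 4 to 24; 28 ± (7 + 7) = 14 to 42. Longest nominal gap 28.

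**Mean wait to the next scheduled test.** Assume a pregnancy is equally likely to become detectable on any of the 84 nominal treatment days. Then mean wait = sum of squared gaps / (2 × 84).

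- Current: 84² / 168 = 42.0 days.
- Week 6 added: (42² + 42²) / 168 = 21.0 days.
- Weeks 2, 6 and 8 added: (14² + 28² + 14² + 28²) / 168 = 1960 / 168 = 11.7 days.

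These waits apply only to a pregnancy that is not noticed and reported first.

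**Expected pregnancies on treatment.** The protocol gives neither the number of women of child-bearing potential nor a contraceptive failure rate. Assume 10 to 30 such women among the approximately 40 subjects, and 0.5% to 5% yearly failure with two methods.

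- Low: 10 × 84 / 365.25 = 2.30 woman-years; × 0.005 = 0.012.
- High: 30 × 84 / 365.25 = 6.90 woman-years; × 0.05 = 0.345.
- Three of four equal arms are active: × 3/4 gives 0.009 to 0.259.

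These count all pregnancies. The unnoticed fraction is unknown, so the relevant number is smaller.

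**False positives from added tests.** Assume a false-positive rate of 0.1% to 1% per urine test (also not in the protocol).

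- Week 6 only: 10 to 30 tests give 10 × 0.001 = 0.01 to 30 × 0.01 = 0.3.
- Weeks 2, 6 and 8: 30 to 90 tests give 30 × 0.001 = 0.03 to 90 × 0.01 = 0.9.

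That is of the same order as, or above, the number of pregnancies expected. What happens after a positive urine test therefore has to be specified.

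**The case against.** The strongest reply is that the protocol contains no error here. It chose prevention plus reporting: exclusions, a serum test at screening, a predose test on Day 1, two methods per couple, and counseling to report. The stop rule was not built on scheduled tests, since it covers female partners of male subjects, whom the trial never tests. Site contact with adverse-event questioning occurs at Weeks 2, 6 and 8, and a site may test on suspicion. All of this stands. A reader might infer that the protocol contradicts itself or that the stop rule cannot work. The documents do not support that: a noticed pregnancy can be reported and acted on, and a subject who stops early is tested at the termination visit. What remains is the pregnancy that passes all these contacts unsuspected.

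A second tempting inference is that, with no test at the Safety Follow-up Visit, a conception late in treatment would be missed for pregnancy and infant follow-up. That goes too far. The reporting request in Section 12.9.6.2 runs for 90 days after the last dose, well beyond the visit at 28 ± 7 days. Such a pregnancy is lost only if it also goes unreported.

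A third objection concerns the remedy. If a positive site urine test led straight to permanent discontinuation, a false positive could remove a subject from a 10-subject arm, and Section 10.5 allows no replacement. This is right, and it shapes the fix. It is also fair that Weeks 6 and 8 can fall as little as 4 days apart, and that the three-visit schedule can still leave a 42-day gap at the extremes of the windows. Week 6 alone gives a worthwhile part of the benefit.

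**Conclusion.** The point holds in a limited form. For a woman of child-bearing potential who completes treatment and whose pregnancy is neither noticed nor reported, no scheduled assessment can trigger the rule in Section 12.9.6.2 until dosing ends. The gap is 84 days nominal (77 to 91), taken directly from Table 3-2. The differing hazard wording in Sections 9.2.7 and 12.9.6 does not change this, because the stop rule applies under either. The statement that oral contraceptive interaction is unstudied is not evidence that VX-509 weakens contraception, and no such claim is made.

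The expected number of cases is well under one: about 0.01 to 0.35 pregnancies of any kind across all arms, resting on the assumed number of women and failure rates. The change should be made because it is cheap and protects patients, not because any analysis is wrong.

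**What to change.** 1. In the Table 3-2 urine pregnancy test row, add a mark at Week 6 at minimum, and preferably at Weeks 2, 6 and 8.
2. In Section 12.9.2, state that the site urine test is also done at these visits and at Week 12. A positive result on treatment leads to immediate interruption of study drug and a confirmatory serum β-HCG test. Permanent discontinuation under Section 12.9.6.2 follows once pregnancy is confirmed. Section 11.3 already allows restart after an interruption for a laboratory abnormality, following discussion with the medical monitor, so a false positive need not end a subject's treatment.
3. Optionally, add a mark at the Safety Follow-up Visit as a backstop to the 90-day reporting request.

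**Cost.** One test per woman on treatment with Week 6 alone, three with Weeks 2, 6 and 8, plus one if the follow-up test is added. With an assumed 10 to 30 women this is 10 to 30 or 30 to 90 on-treatment tests, plus 10 to 30 for the option. If all 40 subjects qualified, the ceilings would be 40 or 120, plus 40. No visits are added. The other cost is an occasional false positive, meaning a brief dosing interruption and a serum test: an expected 0.01 to 0.3 with Week 6 alone, or 0.03 to 0.9 with three visits, under the assumed rates.

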5 LIST OF ABBREVIATIONS

Abbreviation	Definition		
5-ASA	5-aminosalicylic acid		
ACR	American College of Rheumatology		
ACR20-CRP (ACR50-CRP, ACR70-CRP)	≥20% (50%, 70%) improvement in disease severity according to the American College of Rheumatology criteria, using C-reactive protein		
ACR20-ESR, ACR50-ESR, ACR70-ESR	ACR20, ACR50, ACR70 assessed using erythrocyte sedimentation rate		
AE	adverse event		
ALT	alanine aminotransferase		
anti-CCP	anti-cyclic citrullinated peptide		
AST	aspartate aminotransferase		
ATC	Anatomical Therapeutic Chemical		
AUC	area under the concentration versus time curve		
AUC ₀₋₁₂	AUC from the time of dosing to 12 hours		
AUC ₀₋₂₄	AUC from the time of dosing to 24 hours		
AUC _{0-τ}	AUC during a dosing interval		
bid	twice per day		
BMI	body mass index		
bpm	beats per minute		
CD	cell of differentiation		
CI	confidence interval		
C _{max}	maximum observed concentration		
C _{min}	minimum observed plasma concentration		
CPAP	clinical pharmacology analysis plan		
CRP	C-reactive protein		
CTCAE	Cancer Institute Common Terminology Criteria for Adverse Events		
CYP	cytochrome P450		
DAS28-4(CRP)	Disease Activity Score 28 using CRP (4-component)		
DMARD	disease-modifying antirheumatic drug		
ECG	electrocardiogram		
eCRF	electronic case report form		
EDC	electronic data capture		

Abbreviation	Definition		
EENT	eyes/ears/nose/throat		
ELISA	enzyme-linked immunosorbent assay		
ESR	erythrocyte sedimentation rate		
EULAR	European League Against Rheumatism		
FACS	fluorescent activated cell sorter		
FAS	Full Analysis Set		
FDA	Food and Drug Administration		
FSH	follicle stimulating hormone		
GCP	Good Clinical Practice		
GPS	Global Patient Safety		
HAQ-DI	Health Assessment Questionnaire – Disability Index		
HDL	high density lipoprotein		
HIV	human immunodeficiency virus		
IA	interim analysis		
IC ₅₀	concentration resulting in 50% of maximum inhibition		
ICH	International Conference on Harmonization		
ID	identification		
IL	interleukin		
IRB	institutional review board		
IVRS/IWRS	Interactive Voice Response System/Interactive Web Response System		
JAK	Janus kinase		
LC/MS/MS	liquid chromatography with tandem mass spectroscropy		
LDL	low density lipoprotein		
max	maximum value		
MCP	metacarpophalangeal		
M-CSF	macrophage colony-stimulating factor		
MedDRA	Medical Dictional for Regulatory Activities		
min	minimum value		
MRI	magnetic resonance imaging		
MTX	methotrexate		
NOAEL	no observable adverse effect level		
NSAID	nonsteroidal anti-inflammatory drugs		
OMERACT	Outcome Measures in Rheumatology Clinical Trials		
OPG	osteoprotegrin		
PD	pharmacodynamic(s)		

Abbreviation	Definition
PK	pharmacokinetic(s)
PIP	proximal interphalangeal
PPD	purified protein derivative
prn	as needed
P-STAT	phosphorylated signal transducers and activators of transcription
q12h	every 12 hours
qd	once daily
QTc	QT interval corrected
RA	rheumatoid arthritis
RAMRIS	Rheumatoid Arthritis Magnetic Resonance Imaging Scoring System
RANK	receptor activator of nuclear factor kappa-B
RANKL	receptor activator of nuclear factor kappa-B ligand
RF	rheumatoid factor
SAE	serious adverse event
SAP	statistical analysis plan
SCID	severe combined immunodeficiency
SD	standard deviation
SF-36	36-item Short Form
SP	sulfapyridine
STAT	signal transducers and activators of transcription
STIR	short tau inversion-recovery
SUSAR	suspected, unexpected, serious adverse reactions
TB	tuberculosis
TEAE	treatment-emergent adverse event
TIBC	total iron-binding capacity
TNF	tumor necrosis factor
TNF-α	tumor necrosis factor-α
ULN	upper limit of normal
vdHmTSS	Van der Heijde Modified Total Sharp Score
WESR	Westergren erythrocyte sedimentation rate
WHO-DD	World Health Organization-Drug Dictionary

6 INTRODUCTION

6.1 Rheumatoid Arthritis

Rheumatoid arthritis (RA) is a chronic inflammatory disease of unknown etiology that affects 0.5% to 1% of adults in the developed nations. RA often causes destruction of joint cartilage and erosion of adjacent bone, resulting in deformity, loss of function, and subsequent joint replacement. Many patients with RA suffer progressive disability over time^{2,3}, pain⁴, work loss⁵, substantial health care costs⁶, and premature mortality.

Although joint pain and inflammation are the primary clinical manifestation of the disease, RA is a systemic illness that can involve virtually any organ system in the body. The hallmark of the disease is synovitis, in which the synovial membrane is characterized by hyperplasia, increased vascularity, and infiltration of inflammatory cells that contribute to the formation of a destructive pannus. Increased levels of proteolytic enzymes are produced, leading to destruction of cartilage matrix molecules and progressive joint damage.

RA therapy focuses on reducing symptoms and delaying progression of structural disease. Nonsteroidal anti-inflammatory drugs (NSAIDs) and corticosteroids may reduce the symptoms of pain, swelling, and stiffness, but do not alter the natural course of the disease. Disease-modifying antirheumatic drugs (DMARDs) have the potential to slow the progression of joint damage and time to disability and thus alter the natural history of RA.

The most widely used DMARD is methotrexate (MTX). Methotrexate inhibits dihydrofolic acid reductase, interfering with DNA synthesis and cellular replication. Although many RA patients initially respond, a substantial number ultimately have an inadequate response, necessitating the addition of other DMARDs. 10,11,12,13 The progression of structural damage may continue on MTX alone. Newer biologic DMARDs such as tumor necrosis factor- α (TNF- α) inhibitor agents are effective in many cases, including the associated joint damage although a proportion of patients do not respond or become refractory to these compounds. These newer agents have been associated with serious infections, and their long-term safety continues to be monitored. Analysis of synovial tissue can be used to evaluate response to different agents, with change in macrophage infiltrate, levels of interleukin-6, (IL-6)/tumor necrosis factor alpha (TNF- α) predictive of effective treatments. Decrease in the resorptive potential of the synovium can be demonstrated by decreased expression of osteoprotegrin (OPG), receptor activator of nuclear factor kappa-B (RANK) and receptor activator of nuclear factor kappa-B ligand (RANKL) (particularly near the pannus-bone interface) in the synovium.

